## 7. Inclusion/ exclusion criteria

Please see table 1 for inclusion/ exclusion criteria for patient participants in Part A and Part B:

Table 1: Inclusion/ exclusion criteria Part A and B (patient participants)

Inclusion criteria	Exclusion criteria

 
• Adult (aged 18 years or over) and competent to provide consent
 
	
 
• Any previous medical condition, other than HNC, which has a known impact
 

 
• Have a diagnosis of recurrent OPC
 
• Have adequate linguistic and cognitive function to participate in interview
 
• English speaking
 
	on communication/ swallowing (Parkinson's Disease, Multiple Sclerosis, cerebral vascular accident (CVA))
--	--

Please see table 2 for inclusion/ exclusion criteria for carers in Part B:

**Table 2: Inclusion/ exclusion criteria carers Part B**

Inclusion criteria	Exclusion criteria

 
• Be carers of patients 18 years or over who have been diagnosed with recurrent OPC
 
• Have adequate linguistic and cognitive function to participate in interview
 
• English speaking
 
	
 
• They do not fulfil all of the inclusion criteria
 

#### **Number of participants**

Part A: 44 retrospective participants will be recruited. Please see section 10 for detailed description of statistical plan including sample size calculation.

Part B: Expected recruitment rates include approximately 20-30 patients (10-15 retrospective patients and 10-15 prospective patients) and 10-20 carers (5-10 carers of retrospective patients and 5-10 carers of prospective patients) or until data saturation occurs- please see data analysis plan in section 11.

## **8. Methodology**

---

#### **Identification of patients**

Sequential patients who are referred to RM for management of newly diagnosed recurrent OPC will be identified from the weekly head and neck multidisciplinary team meeting. Those patients identifying all of the inclusion criteria and who are invited to an appointment at the Royal Marsden will be sent an initial letter of invitation prior to their appointment. At their appointment they will be approached to take part in the study.

Patients who have undergone surgery at least 12 months ago or who have commenced palliative treatments within the last 12 months will be identified from outpatient clinic lists and will be invited to take part in semi structured interviews investigating their experience of being diagnosed with and

treated for recurrent OPC. Carers/ family members of the person with recurrent OPC will also be invited to take part in an interview. Participant identification centres (PICs) will also be used as part of the recruitment strategy for the study. These centres will identify potential participants through database searches and direct these patients to the recruiting site for participation.

### **Sampling**

Purposive sampling will be used to try and recruit patients who are undergoing/undergone the various treatment options available- open surgery, TORS, re-irradiation, palliative systemic treatments, to ensure that there is a range of patients, both male and female, with representation across a range of ethnic and socioeconomic backgrounds for both Parts A and B of the study.

### **Informed consent**

Potential participants who are receiving care at the Royal Marsden will receive a letter of invitation prior to their next scheduled appointment highlighting that they may be approached about the study in advance of their appointment.

At the patients next scheduled outpatient appointment; which may be virtual or face-to-face, their usual care team will introduce the trial with the patient. PICs will also identify potential participants through database searches and direct these patients to the recruiting site for participation. If the patient expressed an interest in being involved, they will be provided with a Patient Information Sheet (PIS) which will include a telephone number and contact email. Patients identified by PICs will be advised to contact the research team using the contact details included in the PIS. Appropriate time will be given to patients and carers to read and digest the information on the PIS. The potential participant may be asked to provide informed consent following a minimum of 1 hour to read the PIS and consider participation. Potential participants will be offered video call facilities to discuss potential participation with their family friend/ relative if they wish.

During the COVID19 pandemic, national guidelines have advised to minimise face-to-face contact with patients and recommended remote consultations. As such, both during the pandemic and for the remainder of the trial, this consent consultation may either be a face-to-face or telephone / video consultation. For participants identified and recruited via PICs – remote consent only will be obtained.

If a remote consent consultation is held patient identification using date of birth and address will be checked during this process. Where possible, there will be two members of the clinical team present for this consultation; one member taking consent and another member present as a witness; however, this is not mandatory for the consent process.

If the patient is eligible, they will be invited to voluntarily provide informed consent to participate in this study. Consent will be taken by a member of the research team/ speech & language therapy team/ research nurse under the supervision of the PI. If the consultation is being conducted face-to-face then consent will be obtained in-person with wet ink signature on the consent form. For remote

telephone / video consultations, verbal consent will be sought and clearly documented in the patients' medical notes. The patient will also be asked to sign a consent form which can be returned to the study team via:

- Post
- Email (the patient should bring the original wet ink copy to their next hospital appointment)
- In person at the patients next face-to-face hospital appointment

Where a patient has been remotely consented, upon receipt of the original wet-ink consent form it will be signed by the member of staff who had discussed the study with the patient and obtained the verbal consent.

At the next possible in-person visit with the RM patient the study team member who carried out the remote consent should countersign the consent form in the presence of the patient. The patients' medical records should be updated to document the entire consent process.

A copy of the signed ICF along with a copy of the PIS will be given to the study participant. An original signed & dated consent form will be scanned and uploaded to the Electronic Patient Record (EPR) for RM patients and a copy will be placed in the investigator site file (ISF).

#### **Subject withdrawal criteria**

A participant can withdraw from the study at any time. No further data will be collected but data previously collected will still be used. Participants will be made aware that their overall medical care will not be affected if they choose not to participate/withdraw from the study at any time.

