## 5. Study objectives

---

[figure not shown]
The primary objective of the study is to measure change in swallowing function over time for patients receiving treatment for recurrent OPC which will be evaluated by a patient-reported outcome (PRO) using the MD Anderson Dysphagia Inventory (MDADI) (Chen et al 2001) comparing change from baseline to 6 months.

Secondary objectives for the study are to:

1. Investigate potential changes in function for up to 6 months using
  - (i) The Performance Status Scale for Head and Neck Cancer (PSS- HN) scale (normalcy of diet, eating in public and understandability of speech scales) (List et al 1990)
  - (ii) the 100 mL Water Swallow Test (100ml WST) (Patterson et al 2011)
  - (iii) the International Dysphagia Diet Standardisation Initiative (IDDSI) functional diet score (Steele et al 2018)
  - (iv) Fibreoptic Endoscopic Evaluation of Swallowing Dynamic Imaging Grade of Swallowing Toxicity (FEES DIGEST) grade (Starmer et al, *in press*)
2. Assess patient-reported QoL and priority concerns using the University of Washington Quality of Life (UW-QoL) questionnaire (v.04) (Rogers et al 1999)

3. Assess patient-reported priority concerns at baseline and 6 months using the Chicago Priority Scale (CPS) (Sharp et al 1999)
4. Report on gastrostomy tube usage up to 6 months
5. Report on survival status up to 6 months
6. To explore patient and carer priority concerns with regards to function and QoL and how these concerns may influence decision making regarding treatment options using semi structured interviews

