### Secondary endpoints

1. MDADI composite score at baseline and 3 and 6, months following surgical or re-irradiation treatment or 3 and 6, months into non-surgical treatment.
2. Mean PSS-HN Normalcy of diet, public eating and speech intelligibility using the PSS-HN scale scores at 3 and 6 months .
3. Median (IQR) IDDSI functional diet score International dysphagia diet standardisation initiative functional diet scale (IDDSI-FDS) at baseline and 3 and 6 months following surgical or re-irradiation treatment or 3 ad 6,months into non-surgical treatment.
4. Mean 100ml WST capacity score score at baseline and 3 and 6, months following surgical or re-irradiation treatment or 3 and 6 months into non-surgical treatment.
5. FEES DIGEST summary score at baseline and 3 and 6 months following surgical or re-irradiation treatment or 3 and 6months into non-surgical treatment.
6. Mean UW-QoL4 composite physical, social and functional scores at baseline and 3 and 6 months following surgical or re-irradiation treatment or 3 and 6 months into non-surgical treatment.
7. Number and percentage of patients ranking of CPS categories (1-12) in order of importance, at baseline and 6 months following surgical or re-irradiation treatment or 6 months into non-surgical treatment
8. Number and percentage of patients still alive at the end of the study
9. Number and percentage of patients using a gastrostomy at each time point at baseline and 3 and 6 months following surgical or re-irradiation treatment or 3 and 6 months into non-surgical treatment.

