### Part A

Part A: The sample size calculation is based on the primary endpoint, change in MDADI scores from baseline and 6 months following diagnosis/treatment of recurrent disease. Previous data has shown that a 10-point between-group difference in MDADI score is clinically significant (Hutcheson et al 2016). This end point has not been measured systematically previously in recurrent disease patients.

Pilot data collected at the Royal Marsden Hospital available for a service evaluation was used to look MDADI score in this cohort of patients. Data based on 10 patients shows a mean composite score of 66.50 at baseline and 52.60 at 6 months with a standard deviation of the difference of 23.68.

With a two-sided alpha of 5% and 95% power a total of 40 participants will be required to complete the paired questionnaires at baseline and 6 months post-treatment (power function, STATA). An additional 4 patients will be recruited to cover for 10% drop out for a total sample of 44 patients. Seventy-five patients are referred to the Royal Marsden Hospital per year with recurrent OPC and this number is set to increase with the on-going developments in robotic surgery, experimental trials and the development of the International Centre for Recurrent Head and Neck Cancer (IReC). Data collection will take place over an 18-month period.

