## 16. Data handling and record keeping

---

All data will be handled in accordance with the UK General Data Protection Regulation (UK GDPR) and the Data Protection Act 2018. The CRFs will not bear the participant's name or other directly identifiable data. The participant's study Identification Number (PIN) only, will be used for identification. The Subject PIN log will be used to cross reference participant's identifiable information. All data from the paper CRFs and questionnaires will be collected in an excel spreadsheet using PINs only.

The ISF and excel spreadsheet, will be stored at the Royal Marsden NHS Foundation Trust. All data will be coded and no identifiable reference to the participants will be held with the data. Paper CRFs and questionnaires and interview transcripts will be stored in locked, fireproof file cabinets. Coded data held electronically will be stored on password protected NHS computers. In the event of remote working, the secured RM sharedrive can be accessed and used by members of the research team employed by the Royal Marsden. Anonymised audio interview data will be transferred securely to an external transcription service.

The investigator site file will include ICFs, questionnaire response forms, and CRFs. The questionnaire responses and CRFs will not bear identifiable information as the anonymous study identification (PIN) number will be used. The ICFs will be stored securely separate to the anonymised data in a locked fire proof filing cabinet held in the SLT department at the Royal Marsden Hospital.

The Royal Marsden NHS Foundation Trust will permit study-related monitoring, audits, REC review, and regulatory inspection(s), providing direct access to source data/documents. Participants are informed of this during the informed consent discussion. Participants will consent to provide access to their medical notes

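### Formal withdrawal ends all data collection, so later survival and gastrostomy status become unknown; a two-level withdrawal rule with explicit consent would keep both for those who agree

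*Combined protocol and SAP*

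**What the plan says.** Section 8, Subject withdrawal criteria, lets a participant leave at any time without effect on care, and then states: "No further data will be collected but data previously collected will still be used". No intermediate option is described.

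Two secondary objectives in section 5 depend on status over follow-up: "Report on survival status up to 6 months" and "Report on gastrostomy tube usage up to 6 months". The matching secondary endpoints in section 6 are "Number and percentage of patients still alive at the end of the study" and "Number and percentage of patients using a gastrostomy at each time point at baseline and 3 and 6 months".

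Table 4 in section 9, which sets the Part A collection schedule, lists neither item, and no section names a data source for them. Section 11, Part A, promises counts and percentages with 95% confidence intervals, but gives no rule for missing data and no denominator for withdrawn patients. Section 14 states that adverse events are not recorded.

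Section 16 says "Participants will consent to provide access to their medical notes". That sentence closes a paragraph about monitoring, audit, ethics review and inspection, and does not mention withdrawal. For participants reached through participant identification centres (PICs), section 8 adds: "For participants identified and recruited via PICs – remote consent only will be obtained".

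**The concern.** Survival and feeding-tube use can be established from clinical records without asking anything of the patient. Section 9 says patients are routinely reviewed at 3 and 6 months, and withdrawal does not alter care, so for many withdrawn patients the information will exist in the clinic. The rule as written stops the study from using it.

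The percentages would then rest on those who stayed. If leaving is related to getting worse, the remaining group is a selected one and the percentages are biased. Section 2 says the results are meant to inform patients choosing between treatments, so readers will take these figures at face value. Without a recorded level of and reason for withdrawal, they also cannot judge how selective the losses were.

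**Working it through.** **1. The plan's own figure.** Section 10, Part A, gives a pilot "mean composite score of 66.50 at baseline and 52.60 at 6 months", an SD of the difference of 23.68, two-sided alpha of 5% and 95% power.
- Difference: 66.50 − 52.60 = 13.90.
- Paired t-test, exact noncentral t: power is 94.65% at n = 39 and 95.15% at n = 40. The stated 40 completers reproduce.
- Drop-out: 40 × 1.10 = 44, as stated. (Dividing instead, 40/0.90 = 44.4, rounds up to 45; this does not matter here.)

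So N = 44. The 10% is general drop-out from the paired MDADI. It is not a formal withdrawal rate, and the documents give none. The number of withdrawals, w, is therefore an assumption below.

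**2. Is lost status recovered elsewhere?**
- Table 4: neither item is listed.
- Section 11, Part A: feeding-tube presence and type are summarised, with no stated collection after withdrawal.
- Appendix 1: the PSS-HN assessor indicates feeding-tube use for patients also eating by mouth, but this assessment stops at withdrawal.
- Section 14: no adverse event records from which a death could be picked up.
- Section 16: notes access, silent on whether it outlasts withdrawal.

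None of these restores the information.

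**3. Uncertainty from unknown status.** With w of N unknown and a patients observed with the outcome, the percentage among all enrolled lies between a/N and (a + w)/N, a band of width w/N.

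| Withdrawals w (assumed) | Band, w/44 |
|---|---|
| 1 | 2.3 points |
| 2 | 4.5 points |
| 4 | 9.1 points |
| 9 | 20.5 points |

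Example: w = 4, with 32 of the 40 remaining patients alive (assumed).
- Reported on remaining patients: 32/40 = 80.0%, Wilson 95% interval 65.2% to 89.5%.
- Bounds for all 44: 32/44 = 72.7% to 36/44 = 81.8%.

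The confidence interval reflects sampling error only; it does not allow for the unknown outcomes. The same band applies to gastrostomy use at 6 months. At 3 months it applies only to those who withdrew before that visit, since earlier data are kept.

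**4. Possible bias.** With survival of 80% in the 40 who remain and s in the 4 who withdraw, the error of the reported figure is 80 − 100 × (40 × 0.80 + 4 × s)/44.

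| s (assumed) | Error of the reported 80% |
|---|---|
| 80% | 0.0 points |
| 50% | 80 − 77.3 = 2.7 points too high |
| 0% | 80 − 72.7 = 7.3 points too high |
| 100% | 80 − 81.8 = 1.8 points too low |

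The direction depends entirely on s, on which the documents say nothing.

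**The case against.** **Withdrawal is not the same as missing an assessment.** The rule applies only when a participant leaves the study. Appendix 3 lets patients stop the water test and treats an unfinished test as a result, and section 9 allows remote review. Someone too tired for questionnaires can stay enrolled and still be counted, and a death on study is not a withdrawal. This stands, and it narrows the problem to formal withdrawals.

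**Cause and direction are not documented.** A reader might infer that patients often withdraw because they deteriorate, so that survival will be overstated. The setting makes this plausible: section 1 cites average survival of four months with best supportive care. But no section gives reasons for withdrawal, and the last row of the second table shows the error can go the other way. The stronger reading is not supported.

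**Existing consent may not reach this far.** A reader might infer from section 16 that participants have already agreed to record follow-up. Its context is oversight, and it does not say that access continues after withdrawal. For PIC participants the notes may also be held elsewhere, which is an inference from their being identified by other centres. Ending all collection may be a deliberate, cautious consent choice. This stands too, so any change needs its own consent wording. The information sheet and consent form were not available to check.

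**Limited consequence.** The affected endpoints are secondary and descriptive, and data gathered before withdrawal are kept. This is correct and bears on priority. It does not answer the fact that, once the rule is applied, nothing in the plan recovers the later status.

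**Conclusion.** The point holds in a limited form. Followed as written, the withdrawal rule makes survival and gastrostomy status unknown after any formal withdrawal, although both are stated 6-month outcomes that need no patient effort, and no other section makes good the loss.

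The size is 2.3 points of uncertainty per withdrawn patient of 44. Four withdrawals would give 9.1 points, taking four as an illustration only. With few withdrawals the effect could be negligible. Bias arises if withdrawn patients differ in outcome from those who remain; that is an assumption here, and its direction is not established. The sample size is unaffected, and the patient-reported MDADI cannot be rescued from records. This is a worthwhile, inexpensive improvement to secondary results.

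**What to change.** Replace the single rule in section 8 with two levels:
1. Withdrawal from questionnaires and tests, with vital status and feeding-tube status at 3 and 6 months still taken from the medical notes if the participant agrees.
2. Full withdrawal, with no further collection.

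Then:
- State this record follow-up explicitly in the information sheet and consent form, without leaning on the section 16 sentence. For PIC participants, include permission to obtain status from the referring team.
- Record the level of withdrawal and any reason the participant volunteers.
- Add vital status and gastrostomy status to Table 4 as notes-based items.
- In section 11, report both percentages with all enrolled patients as the denominator and show the number unknown.

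The cost is a protocol and consent amendment, a few record checks, and brief contact with referring teams. Participants who have already consented can be followed this way only if they agree, so some gaps may remain. The right to leave completely is preserved.

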## **9. Data Acquisition**

---

### **Part A**

Following informed consent, patients will have all functional and QoL measures collected at their next scheduled outpatient appointment. No additional outpatient appointments or patient contacts will be required for RM patients. All patients are routinely seen by the clinical team at baseline, and for regular follow up including 3 and 6 month clinical reviews, where all measures except the Chicago Priority Scale (CPS) will be repeated. The CPS will be completed at baseline and 6 months only. In the event that social distancing measures remain in place and patients are not attending the hospital for face-to-face review with their clinical team, or if the patient has a preference for remote review, and for participants identified via PICs, a video consultation will be set up so that a minimum set of outcome measures can be collected including the MDADI, and UWQoL4, PSS- HN (all domains), Functional IDDSI Diet Score, CPS and the 100ml WST.

The only measure which cannot be obtained via remote means is the FEES assessment. Please see figure 2 for data acquisition schema.

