**Table 4: data acquisition time points part A**

Timepoint	Measure	Domain	Endpoint
Baseline, 3, and 6 months	MDADI	Swallowing related QoL	Composite score
	UW-QoLv4	Health related QoL	Composite scores of physical and social-emotional functioning are derived from 12 domains. Patients can also highlight up to 3

			priority concerns from the previous 7 days
PSS-HN	Normalcy of Diet, Eating in public and speech intelligibility	Score for each subset	
100ml WST	Swallowing function	Swallowing capacity score (mls/second)	
Functional IDDSI diet score	Diet modification	Diet score (1-8)	
FEES- DIGEST (only if patient is attending for a face-to-face appointment	Swallowing toxicity rating	Summary score (0-4)	
Baseline & 6 months	Chicago priority scale	Patient priority rating of treatment outcomes	Ranked 1-12 priorities

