### Part A

Baseline patient characteristics (age, gender, ethnicity and previous HNC treatment history) will be summarized in addition to the diagnostic and treatment details (site of recurrence, type of treatment, use of reconstruction, tracheostomy, feeding tube presence/ type) using descriptive statistics.

The primary endpoint data will be analysed to compare the mean change from baseline MDADI composite score to 6 months into or post treatment using a two-sided paired t-test if data are normally distributed. In the event of not normally distributed data non-parametric-methods (Wilcoxon Signed Rank test) will be used.

Secondary endpoints (PSS, 100ml WST, IDDSI functional diet score, FEES-DIGEST and UW-QOL, and CPS scores) will be summarised using summary statistics (mean with standard deviation if data are normally distributed or median with IQR if data have a skewed distribution). Counts and percentages will be presented with 95% confidence intervals.

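### FEES-DIGEST is scored only at face-to-face visits, and no within-patient summary is planned, so patients who switch visit mode can make the visit-wise scores differ with no true change (low priority)

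*Combined protocol and SAP*

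**What the plan says.** **Where FEES can be done.** Section 9, Part A: "The only measure which cannot be obtained via remote means is the FEES assessment". Table 3, which lists the remote measures, leaves FEES-DIGEST out. Table 4 marks it "only if patient is attending for a face-to-face appointment".

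**Who is seen remotely.** The same section gives three routes: continuing social distancing, the patient's own choice, and identification by a participant identification centre (PIC). On the last two it reads: "or if the patient has a preference for remote review, and for participants identified via PICs, a video consultation will be set up". The first two can apply at one visit and not at another.

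**What is to be reported.** Section 6, secondary endpoint 5: "FEES DIGEST summary score at baseline and 3 and 6 months following surgical or re-irradiation treatment", with matching time points for non-surgical treatment. It serves secondary objective 1 in Section 5: "Investigate potential changes in function for up to 6 months using" a list of measures that includes FEES-DIGEST.

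**How it is analysed.** Section 11, Part A: "Secondary endpoints (PSS, 100ml WST, IDDSI functional diet score, FEES-DIGEST and UW-QOL, and CPS scores) will be summarised using summary statistics", by mean or median according to distribution. A paired comparison is specified for the MDADI only. The section gives no FEES denominator, no set of patients common to the visits, and no handling of visits without FEES. A flow diagram of patients is planned, but nothing says it will show FEES availability by visit.

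**The concern.** The objective is about change, but the planned output is a separate summary at each visit. For a measure taken in everyone at every visit, the difference between visit means equals the mean within-patient change. For FEES-DIGEST that equality fails once a patient is scored at one visit and seen remotely at another. These patients are alive and in follow-up, so the gap is built into data collection and is separate from death or withdrawal.

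If the choice to attend in person is related to swallowing (for example, less well patients travel less, or patients with problems come in for review), the patients scored at 6 months are a different selection from those scored at baseline. The visit-wise scores can then suggest recovery or deterioration that did not occur. FEES-DIGEST is the study's only instrumental swallowing measure, and Section 2 says the results are meant to inform patients' treatment choices.

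**Working it through.** **Is there a figure in the plan to reproduce?** Not for this endpoint. The only sample-size figures (Section 10: 40 completed pairs, 44 recruited) concern the MDADI. A paired t-test with difference 66.50 − 52.60 = 13.90, SD of the difference 23.68 and two-sided 5% alpha has 95.15% power at 40 pairs, so the 40 reproduces. It has no bearing on FEES. Only the 44 is borrowed below, as a cohort size.

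**Which patients can cause a false change?**
- *Face-to-face at both visits:* in both summaries, so no shift in composition.
- *Remote at both visits, including PIC participants:* in neither summary. They limit whom the result describes but cannot make the two visits differ.
- *Face-to-face at one visit, remote at the other:* in one summary only. This is the group that can move the visit-wise result.

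**Illustration.** From the documents: 44 patients and the 0 to 4 scale. Assumed: 22 patients at grade 1 and 22 at grade 3, all with FEES at baseline, and no patient's grade changing by 6 months. Let p1 and p3 be the proportions of the grade 1 and grade 3 patients attending in person at 6 months.

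- Number scored = 22·p1 + 22·p3
- Mean = (1·22·p1 + 3·22·p3) / (22·p1 + 22·p3)
- Share at grade 3 = p3 / (p1 + p3)

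At baseline the mean is (22 + 66)/44 = 2.00, with 50% at grade 3. At 6 months (expected numbers):

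| p1 | p3 | Scored | Mean | Shift in mean | Grade 3 |
|---|---|---|---|---|---|
| 0.8 | 0.8 | 35.2 | 2.00 | 0.00 | 50% |
| 0.9 | 0.6 | 33.0 | 59.4/33.0 = 1.80 | −0.20 | 40% |
| 0.8 | 0.4 | 26.4 | 44.0/26.4 = 1.67 | −0.33 | 33% |
| 0.6 | 0.9 | 33.0 | 72.6/33.0 = 2.20 | +0.20 | 60% |
| 0.4 | 0.8 | 26.4 | 61.6/26.4 = 2.33 | +0.33 | 67% |

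The true change is zero in every row, and so is the within-patient change in patients scored twice. The visit-wise shift is zero only when attendance is unrelated to grade (first row).

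**When selection is the same at both visits.** If p1 = 0.8 and p3 = 0.4 applied at baseline as well, both means would be 1.67 and the shift zero. The level would still differ from the cohort's 2.00.

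**What pairing does not remove.** With p1 = 0.9 and p3 = 0.6, the paired set is 19.8/33.0 = 60% grade 1 patients, against 50% in the cohort. If true change differed by severity, the paired result would carry that 60:40 weighting.

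**The case against.** The strongest case against is that the plan is open about the restriction. Table 4 attaches the face-to-face condition to the row that defines the FEES endpoint, and Table 3 omits FEES. Read with endpoint 5, the measure is defined for attenders. Section 9 also describes routine clinic review at baseline, 3 and 6 months, with remote review as the alternative, so switching may be uncommon. The study is exploratory, endpoint 5 is one of nine secondary endpoints, and no test is planned for it. Much of this stands, and it is why the priority is low. It does not supply a denominator or a within-patient summary, and knowing that only attenders are scored does not show whether the same people attended each time.

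Three stronger readings are tempting, and the documents do not support them.

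- *That the plan presents FEES-DIGEST as a result for the whole cohort.* It nowhere says so. It leaves the denominator unstated.
- *That PIC participants produce the false change.* They are seen by video and so enter neither visit's summary. Their absence is a matter of representativeness.
- *That the remote share times the attender-versus-remote gap measures the bias in change.* With 40% remote and high grades in 30% of attenders against 10% of remote patients (all assumed), this gives 0.4 × 20 = 8 points. That is the difference between attenders and the cohort at one visit. Bias in change is the later selection bias minus the baseline one, and the two can cancel.

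**Conclusion.** The point holds as a gap in the analysis text. Followed as written, the plan answers a question about change with visit summaries that may come from different patients. A spurious shift needs two things: patients who switch mode between visits, and switching related to severity in a way that differs between visits. The documents permit the first and are silent on the second.

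Size and direction cannot be stated. No remote share, grade distribution or link between attendance and severity is given. The shifts of up to 0.33 grade in either direction come from assumed inputs and show only that the effect need not be trivial on a 0 to 4 scale.

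A reader might infer that the main result is compromised as well. It is not: the MDADI can be collected remotely and its analysis is paired, so the FEES gap does not reach the primary endpoint.

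**What to change.** Amend endpoint 5 in Section 6 and the secondary-endpoint paragraph in Section 11, Part A, as follows.

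1. Define the FEES-DIGEST change result as the within-patient change in patients with FEES at both baseline and the later visit, separately for 3 and 6 months.
2. Keep the per-visit summaries as descriptive results, so that single-visit FEES data are not lost. Give the number in follow-up and the number with FEES beside each.
3. State that PIC participants and patients reviewed remotely are not represented.
4. Tabulate same-visit MDADI, PSS-HN normalcy of diet and IDDSI scores for patients with and without FEES. All three are planned in both modes, so they show the direction of selection. The water swallow test is less suitable because its SOP excludes patients advised to stay nil by mouth.

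The cost is mainly wording and one table, with no extra visits or procedures. No section says that visit mode or the reason for a missing FEES is recorded, so one CRF field may be needed. The downsides are fewer patients in the change result, a narrower claim, and remaining selection of patients who attend in person twice, which items 3 and 4 disclose but do not remove.
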